- b. The number and frequency of nCLE procedure-related AE/SAE from the start of the procedure until end of 12-month follow-up
- 8. To assess the reproducibility of nCLE criteria to the reference standard. Three nCLE characteristics for the detection of malignancy were identified during Wijmans et al. study [10]:
 - a. Dark enlarged pleomorphic cells;
 - b. Dark cell clusters consist of overlapping cell structures ('dark clumps') and
 - c. Continuous movement of the cells in one direction ('directional streaming').
- 9. To create an nCLE image atlas for malignant characteristics in PPNs.

3. Study Design

This is a randomized, controlled, interventional, comparative prospective multi-center study. In total, a maximum of 118 consecutive patients with a (suspected) PPN who are referred for a diagnostic bronchoscopic (Robotic-guided TBNA) procedure will be considered for enrollment. The estimated duration of the study is 24 months. Patients will be consecutively recruited and randomly assigned to undergo Robotic-guided TBNA (n=59) or Robotic-nCLE-guided TBNA (n=59).

Only patients in the nCLE arm will receive intravenously administered fluorescein before the start of the Robotic procedure. During the nCLE procedure, an 18G needle enters the targeted tissue, followed by an nCLE AQ-Flex™ 19N Confocal Miniprobe™ (Mauna Kea Technologies, France) through the biopsy needle, to obtain real-time imaging. nCLE imaging will be performed in the PPNs with a total estimated time for research measurements of 10 minutes. nCLE imaging will be performed for each sequential TBNA pass/sampling within the lung nodule lesion and each TBNA path cytopathological result will be correlated with the nCLE sequence acquired for that TBNA pass. TBNA sampling will end when sufficient diagnostic material will be found with ROSE (as assessed by the cytopathologist) or when the physician performing the procedure judges that the number of samplings/passes is adequate. ROSE will be performed by a cytopathologist.

4. Study Population

Population (base)

Patients with a PPN referred for diagnostic bronchoscopic/endosonographic workup tissue sampling based on standard (PET-) CT imaging

Inclusion criteria

To be eligible to participate in this study, a study subject must meet all of the following criteria:

- ≥ 21 years of age
- Suspected PPN
- Nodule size in CT between 8 mm and 30 mm (largest dimension)

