2. First-two-passes cumulative diagnostic yield is calculated as the proportion of patients for which first-two-passes cumulative TBNA pass during the bronchoscopic procedure yielded a definitive diagnosis out of the total number of patients that have received a diagnostic procedure.
3. First-three-passes cumulative diagnostic yield is calculated as the proportion of patients for which first-three-passes cumulative TBNA pass during the bronchoscopic procedure yielded a definitive diagnosis out of the total number of patients that have received a diagnostic procedure.
4. Etc.... until the fifth pass.

The number of patients has been calculated to demonstrate an increase of the TBNA first-pass diagnostic yield by 20%, from 70% to 90%, between the Robotic-guided TBNA and the Robotic-nCLE-guided TBNA, with a statistical power of 80% with a 2-sided significance level of 0.05. A group size of 59 patients per arm has been derived. By including 59 patients in each arm, we expect to image at least 29 malignant nodules (prevalence of 0.5) in each arm.

The study will enroll 118 consecutive patients randomly assigned 1:1 to Robotic-guided TBNA arm or Robotic-nCLE-guided TBNA arm.

5. Treatment of Subjects

Investigational product/treatment

In recent years, confocal laser endomicroscopy (CLE) has emerged as a novel technique that enables *in vivo* microscopic analysis during ongoing endoscopy [24]. CLE is based on tissue illumination with a low-power laser with subsequent detection of the fluorescence light reflected from the tissue. It is a contrast-based technique, the most widely used agent being the intravenously administered fluorescein. The probe of the endomicroscopy system consists of a flexible catheter probe representing a bundle of optical fibers linked to a micro-objective, a laser scanning unit, and the control and acquisition software (Cellvizio® I.V.E system, Mauna Kea Technologies, France). The principle of the technique is based on a laser beam of the defined wavelength being focused towards the targeted tissue, and the recaptured signal is displayed as 'optical biopsies' in a single horizontal plane.

[figure not shown]

Figure 1: A- Locking of the CLE probe to the aspiration needle. B- CLE probe inside endosonography needle. C- Endosonography images of n-CLE measurements (white arrow) inside a lymph node (LN) (Wijmans/Annema et al. [10]).

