nCLE requires the administration of exogenous fluorescent contrast. Minutes before CLE positioning, the patient will be administered 2.5 mL of 10% fluorescein IV. A repeat dosage of 2.5 ml of 10% fluorescein can be provided after 15-30 minutes to a maximum dosage of 5 ml of 10% fluorescein in total. Patients will be monitored for allergic reactions, including anaphylaxis. Fluorescein Sodium can be used as a contrast agent with Cellvizio® I.V.E system with Confocal Miniprobes™ without change of formulation, mode of action, approved dose, or route of administration. Refer to the indications for using the fluorescein to perform the injection or to chapter 1: "Fluorescein Angiography: Basic Principles and Interpretation" of Ryan et al. book on Optical Imaging Technologies [25].

The target area will then be identified on the ultrasound and/or fluoroscopy monitor and accessed in the usual manner per standard of care. Once the nodule is localized, an 18G needle with the Confocal Miniprobe™ inside will be introduced through the bronchoscope's working channel and advanced into a lung nodule. After the puncture, the AQ-Flex™ 19 N Confocal Miniprobe™ will then be advanced through the needle into the nodule. Imaging will take place, which will be evaluated by the physician performing the procedure. The on-site image interpretation will be recorded. The AQ-Flex™ 19 N Confocal Miniprobe™ will be removed, and tissue will be aspirated at the imaging site from the tip of the needle that is still in place. ROSE will be performed by the cytology team per standard of care. If no lesional tissue is identified, then the robot may be repositioned for additional needle passes. For each needle pass, a separate CLE movie will be recorded. Multiple needle passes and nCLE imaging may occur, specifically if no tumor is identified on ROSE. In the case of re-localization of the needle, nCLE imaging may be repeated before further needle aspirations. Duration will be recorded after each pass. Chest ultrasound or fluoroscopy will be performed to evaluate for pneumothorax.

7. Puncture the identified target lesion with the needle per standard of care and usual procedure (the Confocal Miniprobe™ is pre-loaded but retracted)	8. Maintain the needle as straight as possible and parallel to the working channel of the scope. (to limit the retraction of the probe within the working channel) Twist the locking device and the probe back onto the needle
	

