- PPV: Probability that malignancy is present when sequential cumulative ROSE passes is positive: $= a/(a + b)$
- NPV: Probability that malignancy is not present when sequential cumulative ROSE passes is negative: $= d/(c + d)$

The same calculations will be performed for the different sequential cumulative nCLE passes. Diagnostic performances for both techniques will be compared using the DeLong and DeLong statistical method [26] with the final diagnosis as the reference diagnosis.

Per patient diagnostic yield (cumulative pass diagnostic yield) and performance calculations

Per patient diagnostic yield of each bronchoscopic procedure (Robotic-guided TBNA and Robotic-nCLE-guided TBNA) is defined as the proportion of patients whose procedure will yield a definitive diagnosis out of the total number of patients that have received that procedure. Two diagnostic yields will be calculated: one for the Robotic-guided TBNA arm and one for the Robotic-nCLE-guided TBNA arm. 95% confidence intervals will be calculated, and the p-value to compare diagnostic yield values between arms.

The diagnostic accuracies of a bronchoscopic procedure (Robotic-guided TBNA and Robotic-nCLE-guided TBNA) will be measured at the end of a follow-up period according to their sensitivities and specificities. The sensitivity test will measure the ability of a technique to correctly identify those patients with the disease (true positive rate). In contrast, the specificity test will measure the ability of the technique to correctly identify those patients without the disease (true negative rate). Sensitivity, specificity, positive predictive value (PPV), and negative predictive value (NPV) will be calculated as the accuracy of the Robotic-guided TBNA and that of Robotic-nCLE-guided TBNA diagnosis (based on final pathology results) compared to the definitive diagnosis based on all available procedures and follow-up.

Where a = true positive, b = false positive, c = false negative, and d = true negative:

- Sensitivity: Probability that a Robotic-guided biopsy will be positive when malignancy is present (true positive rate): $= a/(a + c)$
- Specificity: Probability that a Robotic-guided biopsy will be negative when malignancy is not present (true negative rate): $= d/(b + d)$
- PPV: Probability that malignancy is present when a Robotic-guided biopsy is positive: $= a/(a + b)$
- NPV: Probability that malignancy is not present when a Robotic-guided biopsy is negative: $= d/(c + d)$

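### Cumulative nCLE accuracy is compared with cumulative ROSE accuracy, although ROSE largely decides how many nCLE looks each nodule receives

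*Combined protocol and SAP*

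**What the plan says.** Section 3 (Study Design) calls for nCLE imaging at each sequential TBNA pass. The list of standard and study procedures in section 5 likewise repeats imaging and sampling together for every pass.

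On when passes end, section 3 states: "TBNA sampling will end when sufficient diagnostic material will be found with ROSE". The same sentence gives a second way to stop: the physician's judgement that enough passes have been made. Section 5 (Steps during the procedure) adds: "Multiple needle passes and nCLE imaging may occur, specifically if no tumor is identified on ROSE". No stopping rule based on nCLE is stated.

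Section 7 (First- and cumulative-pass diagnostic yields and performance calculations) defines sensitivity, specificity, PPV and NPV for sequential cumulative ROSE passes. It then says "The same calculations will be performed for the different sequential cumulative nCLE passes" and compares the two techniques by the DeLong method, with the final diagnosis as reference.

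The plan does not say how several nCLE looks at one nodule become a single cumulative result. For accuracy, it also does not say how a patient whose sampling stopped before pass k counts at pass k.

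**The concern.** The number of chances given to one test depends on the results of the test it is compared with. In a malignant nodule, a negative ROSE pass tends to lead to another pass, so ROSE can correct its own miss. If nCLE misses at a pass where ROSE is positive, sampling can end there and the miss stands. In a benign nodule, ROSE shows no tumor, so sampling may run longer. Under some scoring rules each extra look is another opportunity for a false-positive nCLE reading.

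The planned comparison treats the number of looks as if it were unrelated to either test's result. At stake is whether a difference between cumulative nCLE and cumulative ROSE reflects the tests or the sampling process. Section 4 (Sample size calculation) says "we expect to image at least 29 malignant nodules (prevalence of 0.5) in each arm", which leaves about 30 of 59 nodules in the nCLE arm to carry specificity, so a few extra false positives would be visible.

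**Working it through.** **The plan's own figure.** The only computed design figure is the sample size: "A group size of 59 patients per arm has been derived", for first-pass yield of 70% against 90%, "with a statistical power of 80% with a 2-sided significance level of 0.05". With unpooled variance, n = (1.960 + 0.842)² × (0.70×0.30 + 0.90×0.10) / 0.20² = 58.87, so 59. It reproduces and is not in dispute. The plan states no figure for cumulative nCLE accuracy or for the number of looks.

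**Inputs from the documents.** One look per pass (sections 3 and 5). Cumulative analysis to five passes (section 4); five is a limit of the analysis, not a stated limit on sampling. Prevalence 0.5 (section 4). The background gives 90% nCLE accuracy in tumors from an earlier study, but no specificity per look.

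**Assumptions.** Looks are capped at five, with a constant probability s of stopping after each pass. Specificity per look is 0.90. A nodule is scored positive if any look is positive. The documents give none of s, the specificity per look or the scoring rule.

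**Distribution of looks.** P(k looks) = (1−s)^(k−1) × s for k = 1 to 4, and (1−s)⁴ for k = 5. If sampling of malignant nodules stops only on a positive ROSE, with probability 0.7 to 0.9 per pass, they average 1.43 to 1.11 looks. Benign nodules average 1.43, 1.94, 2.77 and 3.36 looks at s = 0.7, 0.5, 0.3 and 0.2.

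**Specificity.** Cumulative specificity = Σ P(k looks) × S(k). With independent looks S(k) = 0.90^k: 0.900, 0.810, 0.729, 0.656, 0.590. With beta-binomial correlation 0.5, S(k) = 0.900, 0.855, 0.827, 0.806, 0.790. For s = 0.5 and independent looks: 0.450 + 0.2025 + 0.0911 + 0.0410 + 0.0369 = 0.82.

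| s after each benign pass | Independent looks | Correlation 0.5 |
|---|---|---|
| 0.7 | 0.86 | 0.88 |
| 0.5 | 0.82 | 0.87 |
| 0.3 | 0.76 | 0.84 |
| 0.2 | 0.71 | 0.83 |
| 0 (five looks in every nodule) | 0.59 | 0.79 |

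With 30 benign nodules, 0.90 means 30 × 0.10 = 3 false positives, and 0.76 means 30 × 0.24 ≈ 7.

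**A different rule.** If five looks are taken and the majority decides, specificity is P(at most 2 of 5 positive, each with probability 0.10) = 0.99.

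**Sensitivity.** Suppose ROSE and nCLE each detect a malignant nodule with probability 0.70 per pass (assumed), independently, that any positive pass counts for either test, and that only a positive ROSE stops sampling before pass five. Cumulative ROSE reaches 1 − 0.30⁵ = 0.998. Cumulative nCLE is Σ P(k looks) × (1 − 0.30^k) = 0.490 + 0.191 + 0.061 + 0.019 + 0.008 = 0.77. Two equally good tests appear far apart because one of them controls the stopping. At 0.80 per look, nCLE reaches only 0.85 to 0.82 when ROSE detects 0.7 to 0.9 per pass, against more than 0.99 with five fixed looks.

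**The case against.** The strongest reply is that ROSE does not set the number of looks alone. The physician may also end sampling, and reads nCLE during the procedure, so nCLE may inform that decision. This stands: the dependence on ROSE is substantial but partial.

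A reader might infer that benign nodules receive the most looks. That is likely, since the background explains that biopsies without tumor cells are often treated as non-diagnostic and may need further passes. The documents do not state it, however. Sampling ends on sufficient material, not on malignancy, so a specific benign finding could end it at the first pass. Section 5 also says extra passes may occur and that imaging may be repeated after the needle is moved, both of which are permissive.

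A reader might also infer that nCLE specificity must fall. That needs any-positive scoring, which the plan never specifies.

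Nor do the documents support the reading that results beyond the first pass describe only patients with negative ROSE. Section 4 defines each cumulative yield over all patients who received a diagnostic procedure. Selection would arise only if the accuracy analysis dropped patients who stopped earlier, and the plan does not say that it will.

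Finally, cumulative accuracy under ROSE-guided sampling does describe nCLE as used in this trial. That is a reason to report it, but not to treat its contrast with ROSE as a like-for-like comparison of tests.

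**Conclusion.** The concern holds in a limited form. The cumulative nCLE and ROSE comparison in objective 5 is asymmetric because ROSE largely governs the number of looks, and nothing in the analysis allows for this. The asymmetry follows from the documents; its size does not.

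For specificity, the range of 0.86 to 0.71 (independent looks) or 0.88 to 0.83 (correlation 0.5), against 0.90 per look, rests on any-positive scoring and on the assumed stopping probabilities. The value 0.59 requires five independent looks in every benign nodule and should not be read as an expected result. The sensitivity illustration further assumes that the two tests are independent and that the physician never stops sampling early.

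The matter is confined to one secondary objective. First-pass nCLE accuracy involves one look per nodule and is untouched, as are the primary endpoint and the sample size. It is worth correcting but does not threaten the trial's main conclusion.

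**What to change.** Before results are seen, amend the analysis plan for objective 5 as follows.

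1. Make first-pass nCLE against first-pass ROSE, on the same nodule and analysed as paired data, the main accuracy comparison. The plan already records each pass separately and stores a separate nCLE movie for each.
2. Report cumulative nCLE accuracy as descriptive, under one prespecified rule for combining looks.
3. Keep all imaged patients in every cumulative denominator, carrying the last result forward for those who stopped earlier. This agrees with the yield definitions in section 4.
4. Tabulate the number of looks by final diagnosis, and note that it depends largely on ROSE.
5. Reconcile the statements that imaging accompanies every pass (section 3 and the procedure list in section 5) with the statement that it may be repeated (section 5, Steps during the procedure).

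No new data are needed. The cost is that the cumulative comparison of nCLE with ROSE, which objective 5 names, becomes descriptive; the wording of the objective should be aligned with that.

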In the present study, we aim to compare the diagnostic yield of Robotic-nCLE-guided TBNA for lung cancer diagnosis to conventional Robotic-guided TBNA using the final diagnosis (histology or follow-up) as the standard reference. Furthermore, we will create an image atlas of the characteristics of nCLE-images in PPNs. Also, we aim to describe tumor types based on in-vivo characteristics. Improved characterization of distal lung lesions might lead to improved and quicker cancer diagnosis and patient care.

Background: nCLE imaging of PPNs under bronchoscopic guidance is feasible and safe.

Primary objective:

To compare the first-pass diagnostic yield of the sequential needle passes (ROSE) between the Robotic-nCLE-guided TBNA arm and the Robotic- guided TBNA arm in PPNs.

Primary endpoint:

Increase of the first-pass diagnostic yield by 20%, from 70% to 90%, between Robotic-nCLE-guided TBNA arm and the Robotic- guided TBNA arm in PPNs.

Secondary objectives:

1. To compare the per-patient diagnostic yield (cumulative pass diagnostic yield: cumulative number of passes until five cumulated passes) of Robotic-nCLE-guided TBNA arm to that of Robotic-guided TBNA arm in PPNs.
2. To compare the proportion of patients with lung cancer treatment in the Robotic-nCLE-guided TBNA arm to that of the Robotic-guided TBNA arm in PPNs.
3. To compare the proportion of patients with follow-up (video-assisted thoracoscopic surgery (VATS) or TTNA or TBNA procedures) in the Robotic-nCLE-guided TBNA arm to that of the Robotic-guided TBNA arm in PPNs.
4. To compare the number of passes needed to obtain a final diagnosis of Robotic-nCLE-guided TBNA to that of Robotic-guided TBNA in PPNs.
5. To assess the diagnostic performance (sensitivity, specificity, PPV, NPV, accuracy) of the sequential cumulative nCLE passes and the sequential cumulative ROSE passes using the final diagnosis as a reference.
6. Feasibility: obtain adequate CLE video footage in >80% of the PPN punctures.
7. To assess the safety of nCLE imaging, as defined by:
 - a. The number and frequency of all AE/SAE from the start of the procedure until end of 12-month follow-up;
 - b. The number and frequency of nCLE procedure-related AE/SAE from the start of the procedure until end of 12-month follow-up.
8. To assess the reproducibility of nCLE criteria with regard to the reference standard. Three nCLE characteristics for the detection of malignancy were identified during Wijmans et al. study [10]:

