The tumor board will determine intermediate diagnosis and management recommendations for each patient at the intermediate and final diagnosis phases (see Figure 3). Three therapeutic management options will be considered: "neither treatment nor follow-up", "follow-up", or "treatment" (see above). If the diagnosis is certain, "neither surgery nor surveillance" will be recommended for benign nodules; treatment will be recommended for malignant lesions; either treatment or follow-up will be recommended for indeterminate nodules.

An intermediate diagnosis and an intermediate management recommendation will be provided after the tumor board receives TBNA histological results and recorded in the Case Report Form for each patient of both arms.

A final diagnosis and a final management recommendation will be provided just after the final diagnosis results are received by the tumor board and recorded in the Case Report Form for each patient of both arms.

These intermediate diagnosis and management recommendations will also be compared to the definitive diagnosis and final patient management decisions.

7. Statistical Analysis

Population demographics comparison in both arms:

Statistical analysis will be performed to compare the patient population in terms of demographics to assess whether there are any differences between the populations of the two arms in terms of age, sex, race, type of lung cancers, and cancer prevalence.

Lesion characteristics comparison in both arms:

Statistical analysis will be performed to compare the lesion characteristics to assess whether there is any difference in lesion characteristics between the two arms, in terms of size, location of the nodule, Presence of bronchus sign on computerized tomography, lung zone, positive PET, associated lymphadenopathy, distance closest to fissure, distance from lesion to pleura, and pre-procedure probability of malignancy.

Navigation Accuracy

Distance between the tip of the locatable guide/nCLE Confocal MiniprobeTM and the targeted lung lesion will be measured for each nodule. The median and standard deviation of the distance will be calculated for both arms. Using a statistical test (Student T-test), they will be compared between arms (Robotic-guided TBNA and Robotic-nCLE-guided TBNA).

Navigation success

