- Accuracy: Probability that a Robotic-guided biopsy gives correct prediction among the total number of cases examined: $= (a + d)/(a + b + c + d)$

Patient diagnostic and management analysis:

Intermediate and final diagnosis and management recommendation proportion differences for the two patient populations (Robotic-guided TBNA arm and Robotic-nCLE-guided TBNA arm) will be compared using a chi-square test. Intermediate and final diagnosis and management recommendation proportions will also be compared for the two patient populations. Differences between Robotic-guided TBNA and Robotic-nCLE-guided TBNA arms regarding the specific diagnostic and management categories will be compared using McNemar's test both at the intermediate diagnosis and the final diagnosis stage.

Feasibility statistical analysis:

The feasibility of needle-based lung cancer diagnosis will be assessed by investigating the following items:

- Assessing nCLE-image quality
- Assessing the feasibility of the integrated needle/Cellvizio® I.V.E Confocal Miniprobe™.

The imaging feasibility yield for the Robotic-nCLE-guided TBNA procedure is defined as the proportion of patients in whom procedure will yield at least good nCLE image quality out of the total number of patients that will receive that procedure.

The mechanical feasibility yield for the Robotic-nCLE-guided TBNA procedure is defined as the proportion of patients for whom Robotic-nCLE-guided TBNA procedure will be possible mechanically (meaning that the nCLE probe will be guided to the nodule successfully) out of the total number of patients that will receive that procedure.

Safety:

The safety will be assessed by carefully monitoring adverse events related to both procedures. Serious adverse event rates will be calculated by dividing the number of events for each procedure divided by the total number of procedures for each arm.

Reproducibility:

To assess the reproducibility of bronchoscopy guided nCLE:

- Estimating the reproducibility of nCLE criteria will be evaluated by calculating the inter-observer agreement of nCLE criteria between 3 readers (Fleiss Kappa).

In Wijmans et al. [10], three nCLE characteristics for the detection of malignancy were identified in different subtypes of lung tumors and metastatic lymph nodes:

- 1) dark enlarged pleomorphic cells;
- 2) dark cell clusters consisting of overlapping cell structures ('dark clumps'); and

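### Final diagnosis is tested between arms as a management result although nCLE cannot change it, and the treated share (objective 2) has no time point and no fixed direction of benefit

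*Combined protocol and SAP*

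**What the plan says.** Section 7, Patient diagnostic and management analysis, plans a chi-square comparison of the arms and adds: "Intermediate and final diagnosis and management recommendation proportions will also be compared for the two patient populations". That covers four quantities: diagnosis and management, each at the intermediate and at the final stage.

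Secondary objective 2 (Summary, and again in the objectives before section 3) is "To compare the proportion of patients with lung cancer treatment in the Robotic-nCLE-guided TBNA arm to that of the Robotic-guided TBNA arm in PPNs". It gives no time point.

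Section 5, Final Diagnosis or Definitive Diagnosis, has later biopsies, surgery, imaging and clinic visits up to 12 months decide whether a nodule is malignant. Section 5, Histological evaluation, says that surgery after a negative bronchoscopy does not depend on the nCLE result.

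Section 7, Population demographics comparison, checks "whether there are any differences between the populations of the two arms in terms of age, sex, race, type of lung cancers, and cancer prevalence".

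Section 6, Diagnostic and Therapeutic Management, has the tumor board record an intermediate diagnosis and recommendation once the TBNA result is known, and a final one later. Treatment is recommended for malignant lesions, and treatment or follow-up for indeterminate ones. It adds: "These intermediate diagnosis and management recommendations will also be compared to the definitive diagnosis and final patient management decisions". Section 8, Patient management, places the three options directly after the TBNA, and the third endpoint in section 8 concerns a correct change in diagnosis and management.

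**The concern.** Whether a nodule is malignant is fixed before randomisation. nCLE may change how soon and how surely that is learned, but once follow-up has settled the question in both arms, the share of malignant final diagnoses describes who was enrolled. The plan uses this quantity twice: as a balance check, and as a between-arm result.

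Treatment at the end of follow-up behaves almost the same way, because most cancers missed at the index procedure may be found and treated later. A treated share also does not say whether the treated patients were the right ones.

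Two errors could follow. A chance imbalance in cancer prevalence could be reported as a benefit or harm of nCLE. Conversely, a real gain in correct early decisions could leave no trace in these comparisons.

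**Working it through.** **Inputs from the plan.** Sample size calculation, section 4: "A group size of 59 patients per arm has been derived", "with a statistical power of 80% with a 2-sided significance level of 0.05", first-pass yield 70% v 90%, 1:1 allocation, malignancy prevalence 0.5 in each arm. The plan gives no cumulative yield, no later-detection rate for missed cancers and no treated share of indeterminate nodules. Those below are assumptions.

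**The plan's own figure.** n = (1.960 + 0.842)² × (0.7×0.3 + 0.9×0.1) / 0.2² = 58.87, rounded up to 59. It reproduces. Exact enumeration of the uncorrected chi-square test at 59 per arm gives 80.5% power. The same enumeration is used below.

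**(a) Final diagnosis.** True share malignant 50% v 50%, expected difference 0.
- Rejection rate 5.3%.
- 95% range of the observed difference: ±1.96 × √(2×0.25/59) = ±18 points.
- Probability of a gap of 10 points or more in either direction: 31%.

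**(b) Treatment at the end of follow-up.** Assume that index detection of cancers is 70% v 90%, a share c of missed cancers is later found and treated, and no one else is treated. Treated share = 0.5 × [Se + (1 − Se) × c].

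| c | Control | nCLE | Difference | Rejection rate |
|---|---|---|---|---|
| 50% | 42.5% | 47.5% | 5 points | 8.7% |
| 80% | 47% | 49% | 2 points | 5.8% |
| 100% | 50% | 50% | 0 | 5.3% |

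Assuming instead that 90–95% of control cancers and 98–100% of nCLE-arm cancers are eventually treated gives differences of 1.5 to 5 points and rejection rates of 6–9%. For 80% power, 95% v 98% would need about 17,420 per arm and 90% v 100% about 1,565.

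**(c) Treatment recommended at the intermediate stage.** Same detection rates, only confirmed cancers treated: 0.5×0.7 = 35% v 0.5×0.9 = 45%. This is a real 10-point difference, with 20% power at 59 per arm.

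**(d) Direction of the treated share.** Now let a share q of indeterminate nodules be treated, with 30% v 10% of patients indeterminate. Treated share = 0.35 + 0.30q v 0.45 + 0.10q, so the difference is 0.10 − 0.20q.
- q = 0: 35% v 45%
- q = 0.5: 50% v 50%
- q = 1: 65% v 55%

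The sign reverses although the diagnostic gain is identical.

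**(e) Agreement of the intermediate recommendation with the final diagnosis, 59 per arm.**
- 70% v 90%: power 80.5%.
- 80% v 90%: power 34%; 95% interval half-width 1.96 × √((0.16 + 0.09)/59) = 12.8 points.

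The first line borrows the first-pass yields. The intermediate recommendation follows the whole procedure, where the plan expects yield to rise with further passes to a plateau, so a smaller gap is plausible. Restricting to final-malignant nodules leaves about 29 per arm, and 70% v 90% would then have 48% power.

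**The case against.** A reader might infer that none of the management comparisons can show an nCLE effect and that any significant result must be chance. The documents do not support that.

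- Objective 2 has no time point, and section 8 considers management directly after the TBNA. Read there, result (c) is a genuine nCLE effect, though underpowered.
- The section 7 sentence also covers the intermediate stage, where randomisation does not make the arms alike.
- The later-detection rate in (b) has no source in the documents. Section 5 leaves follow-up to the practitioner's judgement, says surgery could follow, counts absence of progression at 12 months as true-negative, and foresees treatment without a confirmed diagnosis. Treatment can therefore depend on how often the TBNA is non-diagnostic, which nCLE is meant to change.
- The plan already has the idea of correctness, in the third endpoint and in the planned comparison of intermediate with final decisions. Objective 3 (later VATS, TTNA or TBNA) is also something nCLE can change.

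All of this stands, and it confines the strong claim to final diagnosis. It does not rescue the test of final diagnosis, give objective 2 a time point or direction of benefit, or supply a between-arm test of correct management, which neither section 7 nor section 8 specifies.

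**Conclusion.** The point holds in three parts.

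1. The between-arm test of final diagnosis has an expected difference of about zero and rejects at about the nominal 5% (5.3% at prevalence 0.5). A significant result would mainly reflect chance imbalance or unequal completeness of follow-up.
2. The final-stage management comparison, and objective 2 if read at the end of follow-up, are nearly uninformative but not strictly null: rejection rates of about 5% to 9% if 50% to 100% of missed cancers are later treated.
3. At any time point the treated share has no fixed direction of benefit, because the outcome for indeterminate nodules is left open.

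The figures rest on the plan's prevalence of 0.5 and on first-pass yields used in place of whole-procedure detection, which the plan does not give. Only secondary analyses are affected; the primary endpoint and its sample size are untouched.

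**What to change.** - Report final diagnosis by arm descriptively, with the other comparability checks, and drop its between-arm test.
- State that objective 2 is read at the intermediate, post-TBNA recommendation. Report the treated share descriptively, split by final diagnosis.
- As the main management comparison, in line with the third endpoint, test by chi-square between arms the proportion of all randomised patients with a procedure whose intermediate recommendation agrees with the final diagnosis. For scoring only, agreement means treatment recommended and final diagnosis malignant, or no treatment recommended and final diagnosis non-malignant. Keep all such patients in the denominator, since the final-malignant subset is only about 29 per arm.
- Label this comparison secondary, report the difference with a 95% confidence interval, and claim no 80% power for it.

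The cost is wording in the objectives and sections 7 and 8. The intermediate and final records are already in the CRF for both arms, so no new data are needed. The downside is that the final-diagnosis and treated-share figures become descriptive.
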